8.5 Risks vs. benefits

We have specifically designed the study intervention and esmolol titration protocol to minimize to the maximal extent possible the risks associated with this study. Based on our preliminary data and an Italian pilot study, we believe that the risk-to-benefit ratio for individual patients is favorable.

9.0 Human Subjects

Each study participant or a legally authorized representative (LAR) must sign and date an informed consent form. Institutional review board (IRB) approval is required before any subject is entered into the study.

9.1 Selection of Subjects

Federal regulations at 45 CFR 46(a)(3) require equity/distributive justice in human subjects research. The participating ICUs will be screened to determine whether any patient meets inclusion and not exclusion criteria, drawing on routine clinical data. No protocol-specific tests nor procedures will be performed as part of the screening process. Potential subjects will not be approached until the clinical team has granted oral permission to approach the patient and/or LAR for informed consent. Study exclusion

criteria neither unjustly exclude classes of individuals from participation in the research nor unjustly include classes of individuals for participation in the research. The recruitment of subjects are therefore equitable/just.

9.2 Justification for Including Vulnerable Subjects

The present research aims to investigate the safety and efficacy of a specific treatment for patients with critical illness. Due to the nature of critical illness, the majority of these patients will have impaired decision-making capabilities. This study cannot be conducted if limited to enrolling only those subjects with retained decisional capacity. Hence, subjects recruited for this trial are not being unfairly burdened with involvement in this research simply because they are easily available.

9.3 Informed Consent

Federal regulations at 45 CFR 46.111(a)(5) require informed consent to participate in research. As ECASSS will enroll critically ill, intubated patients, the large majority of initial consents will be from the subject's LAR, and thus the remainder of this section will focus on LARs. The investigator is responsible for ensuring that the LAR understands the risks and benefits of participating in the study, and answering any questions the LAR may have throughout the study and sharing any new information in a timely manner that may be relevant to the LAR's willingness to continue the subject's participation in the trial. The consentor will make every effort to minimize coercion, including not allowing a Study Investigator to participate in obtaining consent when s/he is currently providing clinical care to the subject. All study participants or their LARs will be informed of the objectives of the study and the potential risks. The informed consent document will be used to explain the risks and benefits of study participation to the LAR in simple terms before the subject is entered into the study, and to document that the LAR is satisfied with his or her understanding of the risks and benefits of participating in the study and desires to participate in the study. The Study Investigator is responsible for ensuring that informed consent is obtained from each subject or LAR. This includes obtaining the appropriate signatures and dates on the informed consent document prior to the performance of any protocol procedures and prior to the administration of study agent.

9.4 Continuing Consent

For subjects for whom consent was initially obtained from a LAR, but who subsequently regain decisional capacity while in hospital, investigators will seek formal re-consent for continuing participation, inclusive of continuance of data acquisition. The initial consent form signed by the LAR will reflect that such consent will be attempted and will be updated when such "re-consent" is obtained.

9.5 Withdrawal of Consent

Patients may withdraw or be withdrawn (by the LAR) from the trial at any time without prejudice. Data recorded up to the point of withdrawal will be included in the trial analysis, unless consent to use their data has also been withdrawn. If a patient or LAR requests termination of the trial drug during the treatment period, the drug will be stopped but the patient will continue to be followed up as part of the trial. If a patient or LAR withdraws consent during trial treatment, the trial drug will be stopped but permission will be sought to access medical records for data related to the trial. If a

patient or LAR wishes to withdraw from the trial after completion of trial treatment, permission to access medical records for trial data will be sought.

9.6 Identification of LARs

Many of the patients approached for participation in this research protocol will be decisionally impaired due to their critical illness. Hence, most patients will not be able to provide informed consent. Accordingly, informed consent will be sought from the participants legally authorized representative (LAR), as defined at 45 CFR 46 102 (c). In this study, LARs will be identified as stipulated by relevant regulations and statutes as required by IRBs, as per the standards defined for clinical decision making, as is the standard practice in human subjects research.

9.7 Confidentiality

Federal regulations at 45 CFR 46 111 (a) (7) requires when appropriate, adequate provisions to protect the privacy of subjects and to maintain the confidentiality of data. To maintain confidentiality, all case report forms and reports will be identified only by a coded number. The coded number will be generated by a computer, and only the study team will have access to the codes. All records will be kept in a locked, password protected computer. All computer entry and networking programs will be done with coded numbers only. All paper case report forms will be maintained inside a locked office.

10 Adverse Events

Patient safety is central to this study protocol. Each investigator is responsible for the safety of the study participants under his/her care. Investigators will determine daily whether any adverse events occurred during the period from enrollment through 24 hours after the completion of the esmolol infusion.

10.1 The following adverse events will be collected in the adverse event case report forms:

- Serious adverse events
- Nonserious adverse events that are considered by the investigator to be related to study drug or study procedures or of uncertain relationship (Appendix 4)
- Adverse events that lead to permanent discontinuation of the study drug infusion. STOP events, as outlined in the titration protocol, are reported separately, recognizing that STOP events often will be related to the underlying septic shock rather than being drug- or protocol-related, as determined by their persistence for more than 20min after discontinuation of esmolol (at which points the effects of esmolol will have resolved). STOP events that require the permanent discontinuation of study drug infusion will be reported as adverse events.

A clinical trial adverse event is any untoward medical event associated with the use of a drug or study procedure in humans, whether or not it is considered related to a drug or study procedure.

After randomization, adverse events related to protocol procedures or occurring after the patient receives the first dose of study drug must be evaluated by the study investigator. If the adverse event is judged to be reportable, the investigator will report to

the SMC his/her assessment of the potential relatedness of each adverse event to study drug or study procedure. Investigators will assess if there is a reasonable possibility that the study drug or procedure caused the event, based on the criteria outlined in Appendix 4. Investigators will also consider whether the event is unanticipated or unexplained given the patient's clinical course, previous medical conditions, and concomitant therapies.

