ECASSS ROLL-IN Study Drug Titration protocol

Fundamental rules for study drug titration:

The target heart rate is 85 bpm. Start study drug infusion at 20 mcg/kg/min, without bolus, if HR \geq 100 bpm. If HR >90 bpm and <100 bpm, start study drug infusion at 10 mcg/kg/min, without bolus. Increase by 20 mcg/kg/min every 20 minutes as long as HR > 90 bpm, to a maximum dose of 100 mcg/kg/min. If HR < 80 bpm and > 70 bpm, decrease infusion rate by 10 mcg/kg/min; if HR ≤ 70 bpm and > 60 bpm, decrease infusion rate by 20 mcg/kg/min. Stop study drug infusion whenever a STOP EVENT occurs. Study drug infusion is completed 3 hours after vasopressor infusions have stopped. The up-titrations can be smaller than stipulated if the clinician and/or investigator feels that a small up-titration is indicated. Up-titrations should not occur during a REASSESS VOLUME STATUS event.

Study drug should be preferentially infused centrally; where no port is available, study drug should **not be** infused into a small peripheral vein or via butterfly catheter.

STOP EVENTS:

1. If HR is ever ≤ 60 bpm, immediately stop infusion for 20 minutes, then restart at half the previous infusion rate, rounded to nearest 10 mcg/kg/min. Do not resume infusion until HR > 70 bpm.
2. If vasopressor dose increases by 0.2 mcg/kg/min norepinephrine (or equivalent) AND doubles within 60 min despite adequate volume expansion, STOP the study drug infusion. Alternatively, if the treating clinician believes that the shock is worsening significantly, STOP the study drug infusion. Do not resume without explicit approval of study physician.
3. If cardiogenic shock develops ($ScvO_2 \leq 60\%$ OR LV Ejection Fraction $\leq 25\%$ OR Cardiac Index ≤ 2.0 L/min/m²), STOP the study drug infusion. Do not resume without explicit approval of study physician.
4. If clinically apparent bronchospasm develops, STOP the study drug infusion. Do not resume.
5. If Grade 2 or Grade 3 heart block develops, immediately STOP the study drug infusion. Do not resume.

REASSESS VOLUME STATUS EVENTS:

When markers of potential preload deficit occur (urine output < 0.5 ml/kg/hr OR vasopressor dosage increase), immediately EVALUATE FOR VOLUME RESPONSIVENESS. A vasopressor dosage increase is defined as at least 0.05 mcg/kg/min absolute AND 20% relative increase in the norepinephrine (or equivalent) infusion.

Titrate vasopressors as per local practice to maintain MAP ≥ 65 mmHg. Norepinephrine is the preferred primary vasopressor.

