Investigators will grade the strength of the relationship of an adverse event to esmolol or study procedures as follows:

- **Definitely Related:** The event follows: (a) a reasonable, temporal sequence from study drug or a study procedure; and (b) cannot be explained by the known characteristics of the patient’s clinical state or other therapies; and (c) evaluation of the patient’s clinical state indicates to the investigator that the experience is definitely related to study procedures.
- **Probably or Possibly Related:** The event should be assessed following the same criteria for “Definitely Related”. If in the investigator’s opinion at least one or more of the criteria are not present, then “probably” or “possibly” associated should be selected.

- Probably Not Related: The event occurred while the patient was receiving esmolol or undergoing study procedures but can reasonably be explained by the known characteristics of the patient's clinical state or other therapies.
- Definitely Not Related: The event is definitely produced by the patient's clinical state or by other therapies administered to the patient.
- Uncertain Relationship: The event does not meet any of the criteria previously outlined.

Certain serious adverse events will not require adjudication; they will always be understood to be drug-related.

[figure not shown]
- Third-degree heart block while receiving esmolol infusion.

A4.3. CLINICAL OUTCOMES THAT MAY BE EXEMPT FROM ADVERSE EVENT REPORTING

Study-specific clinical outcomes of septic shock, as outlined in Sections 2.8 and 3.5 (Primary and Secondary Outcomes) and Section 5.1 (Assessments) are exempt from adverse event reporting unless the investigator deems the event to be related to the administration of study drug or the conduct of study procedures (or of uncertain relationship). The following are examples of events that will be considered study-specific clinical outcomes

- Death not related to the study drug or procedures.
- Cardiovascular events: changes in doses of vasoactive drugs or VOLUME EXPANSION events.
- Organ dysfunction events: changes in the SOFA score and its constituents.
- Cardiogenic shock that does not resolve 20 minutes after cessation of esmolol

A4.4. DECISION TREE FOR REPORTING ADVERSE EVENTS

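### Section 10.1 uses persistence beyond 20 minutes off esmolol to attribute a STOP event to septic shock, which conflicts with A4.2 for third-degree heart block and with the Appendix 4 relatedness criteria

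*Combined protocol and SAP*

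**What the plan says.** Section 10.1 has STOP events reported separately from other adverse events. The reason given is that they will often be due to the underlying septic shock "rather than being drug- or protocol-related, as determined by their persistence for more than 20min after discontinuation of esmolol". The basis for the 20 minutes is added in brackets: "at which points the effects of esmolol will have resolved". The same item ends: "STOP events that require the permanent discontinuation of study drug infusion will be reported as adverse events".

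Other parts of the protocol bear on the same judgement:

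- Appendix 1, STOP event 5: "If Grade 2 or Grade 3 heart block develops, immediately STOP the study drug infusion. Do not resume".
- A4.2: "Certain serious adverse events will not require adjudication; they will always be understood to be drug-related". The one entry visible on that list is "Third-degree heart block while receiving esmolol infusion", with no condition on how long the block lasts.
- The last paragraph of Section 10.1 tells investigators to judge whether the drug or a procedure could reasonably have caused the event, using the Appendix 4 criteria.
- A4.3 gives cardiogenic shock still present 20 minutes after esmolol stops as an example of an outcome exempt from adverse event reporting, unless the investigator considers it related or of uncertain relationship.

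**The concern.** The plan appears to hold two causal tests for the same events. One is the graded assessment in A4.2, with its automatic attribution. The other is the 20-minute test in 10.1, which treats non-reversal as evidence against the drug.

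The second test is a weak inference. That esmolol's effect has gone by 20 minutes says something about what sustains an event at that point. It does not say what started it. Section 8.1 assumes that esmolol's theoretical side effects all reverse within minutes of stopping. If an event that fails to reverse is for that reason put down to sepsis, the roll-in cannot produce evidence against that assumption.

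The label matters because the study has a single arm and at most 10 patients. No control rate exists against which a misattributed event would show up, and several reporting routes depend on relatedness.

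**Working it through.** The documents derive no figure on this point, so the check compares the texts and traces what relatedness controls.

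**1. The contradiction.** Suppose third-degree block begins during infusion and lasts 25 minutes after the stop (an illustrative duration).

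- Appendix 1 makes it STOP event 5.
- Under the 10.1 clause, 25 > 20 minutes, so it is attributed to septic shock.
- Under A4.2 it is drug-related without adjudication.

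The two answers are opposite, and the visible text gives no order of precedence.

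**2. The wider conflict.** The A4.2 grades weigh temporal sequence, explanation by the patient's condition or other therapy, and the investigator's evaluation. No time-to-resolution test appears among them. For the other STOP events, 10.1 therefore adds a criterion that the governing appendix does not contain.

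**3. What relatedness controls.**

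- Section 10.2 and Appendix 4: the 24-hour alert to the SMC chair is for events that are both serious and related.
- Appendix 4: a SUSAR must first be a suspected adverse reaction, so it needs a reasonable possibility of drug causation.
- Section 10.1: a nonserious event reaches the adverse event form only if it is related, of uncertain relationship, or leads to permanent discontinuation.

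**4. Exposure by STOP event, if it is nonserious and called unrelated.**

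| STOP event (Appendix 1) | Can infusion resume? | Still on the adverse event form? |
|---|---|---|
| 1. Heart rate at or below 60 | Yes, under stated conditions | Not if infusion resumes |
| 2. Vasopressor escalation or worsening shock | With study physician approval | Only if the stop is permanent |
| 3. Cardiogenic shock | With study physician approval | Only if permanent, and A4.3 may exempt it when unresolved at 20 minutes |
| 4. Bronchospasm | No | Yes |
| 5. Grade 2 or 3 heart block | No | Yes |

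For items 4 and 5 the form is secure whatever the attribution. For them the exposure is the relatedness label and, when serious, the alert and SUSAR routes. For items 1 to 3 the form itself can depend on attribution. The A4.3 exception does not close this gap, because it also turns on the investigator's view of relatedness.

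**5. Scale.** Event rates are not given, so these counts are assumptions. Take all 10 patients as infused and use exact (Clopper-Pearson) 95% intervals:

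- 1/10 = 10%, interval 0.3% to 44.5%.
- 0/10 = 0%, interval 0% to 30.8%.

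Moving one event takes the first result to the second. Starting from 2/10 (2.5% to 55.6%), it gives 1/10.

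**The case against.** The strongest reply is that the 10.1 clause is a rationale and not a rule. It explains why STOP events are reported separately, and it says only that they will often be septic. The operative instruction comes later in the section and points to Appendix 4, where an investigator may choose possibly related or uncertain for a persistent event. A4.2 is specific and absolute, so it would naturally prevail for third-degree block. Response to stopping a short-acting drug is also reasonable evidence on causality.

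Much of this stands. The word often does soften the clause, but the wording of the persistence condition still reads as a test, and an investigator could apply it as one.

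The safeguards are also real. SAEs are collected during infusion and for 24 hours after, whatever the cause. Permanent-stop events are reported. The SMC has full data access with reviews at 3 and 6 patients, and deaths during infusion go to its chair within 24 hours (Section 6.2).

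Three stronger readings are tempting and not supported:

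- *The most serious events leave the drug-related count.* The plan defines no such count, and the safeguards above keep these events in view.
- *All STOP events contradict A4.2.* Only third-degree block is on the visible always-related list.
- *Appendix 1 itself foresees drug-induced bradycardia beyond 20 minutes.* "Do not resume infusion until HR > 70 bpm" is a restart condition. A rate of 61 to 70 bars restart but no longer meets the STOP threshold, and the sentence says nothing about cause.

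Part of the A4.2 list and the A4.4 decision tree are figures that could not be read. They may name further events or settle precedence.

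**Conclusion.** The point holds as an internal inconsistency with a possible effect on safety attribution. The opposite answers are certain on the visible text for one event type: third-degree heart block that starts on esmolol and is still present more than 20 minutes after the stop. For the other STOP events, the clause competes with the Appendix 4 criteria without directly contradicting the always-related list.

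The consequence is that a persistent drug-triggered event can be labelled unrelated and so miss the 24-hour alert, SUSAR classification or, in the nonserious and non-permanent case, the adverse event form. It is not that such events vanish from the study. No percentage can be attached, because the documents give neither the frequency of STOP events nor how often they persist.

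The conclusion assumes that investigators would read the clause as a test, and that the unseen parts of A4.2 and A4.4 contain no precedence rule. If they do contain one, the sentence in 10.1 should still be brought into line with it.

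**What to change.** - In Section 10.1, delete the clause that makes persistence beyond 20 minutes the determinant of attribution, together with the bracketed explanation attached to it.
- State there that the relatedness of every STOP event is judged by the Appendix 4 criteria, and that the automatic attribution in A4.2 overrides that judgement for the events it lists.
- Reconcile the 20-minute cardiogenic shock example in A4.3 with this wording and with the 10.1 sentence on permanent discontinuation.
- Record time from stopping esmolol to resolution as a data item for each STOP event. Give the SMC all STOP events tabulated as resolved within 20 minutes or not. The information behind the 20-minute idea is then kept as evidence and does not settle the cause in advance.

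A default of related unless an independent cause is documented would not work here, since every patient has septic shock and the exception would always be available.

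The cost is a few sentences, one added field and one table. More events may be labelled possibly related or uncertain, in at most 10 patients. No dose, titration step or stopping criterion changes.

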10.2 SERIOUS ADVERSE EVENTS

Serious adverse event collection begins after the patient or LAR has signed informed consent and has received study drug or undergone study procedures. If a patient experiences a serious adverse event after consent, but prior to receiving study drug, the event will NOT be collected unless the investigator feels the event may have been caused by a study procedure.

Investigators must alert the chair of the SMC of any **serious and study drug or study procedure related** adverse event within 24 hours of investigator awareness of the event. Alerts issued via telephone are to be immediately followed with official notification on the adverse event case report form. See Appendix 4 for reporting timelines for serious, unexpected, study related events (SAEs) and serious, unexpected suspected adverse reactions (SUSARs).

As per federal definitions (primarily in 21 CFR 312.32(a)), a **serious** adverse event is any adverse event that results in one of the following outcomes:

- Death
- A life-threatening event, one that places the subject at immediate risk of death (this does not include an event that, had it been more serious, would have placed the subject at immediate risk of death)
- Prolonged inpatient hospitalization or rehospitalization
- Persistent or significant disability/incapacity, indicating a substantial disruption of a person's ability to conduct normal life functions (i.e., the adverse event resulted in a significant, persistent or permanent change, impairment, damage or disruption in the patient's body function/structure, physical activities and/or quality of life).

Important medical events that may not result in death, be life-threatening, or require hospitalization may be considered serious adverse events when, based upon appropriate medical judgment, they may jeopardize the patient and may require medical or surgical intervention to prevent one of the outcomes listed in this definition.

Given the short-acting nature of esmolol and the limited duration of the study infusion, surveillance for adverse events will extend through 24 hours after completion of the esmolol infusion. Serious adverse events will be collected during and for 24 hours after the esmolol infusion, regardless of the investigator's opinion of causation. Thereafter, serious adverse events are not required to be reported unless the investigator feels the events were related to study drug or a protocol procedure.

APPENDIX 1

ECASSS ROLL-IN Study Drug Titration protocol

Fundamental rules for study drug titration:

The target heart rate is 85 bpm. Start study drug infusion at 20 mcg/kg/min, without bolus, if HR \geq 100 bpm. If HR >90 bpm and <100 bpm, start study drug infusion at 10 mcg/kg/min, without bolus. Increase by 20 mcg/kg/min every 20 minutes as long as HR > 90 bpm, to a maximum dose of 100 mcg/kg/min. If HR < 80 bpm and > 70 bpm, decrease infusion rate by 10 mcg/kg/min; if HR ≤ 70 bpm and > 60 bpm, decrease infusion rate by 20 mcg/kg/min. Stop study drug infusion whenever a STOP EVENT occurs. Study drug infusion is completed 3 hours after vasopressor infusions have stopped. The up-titrations can be smaller than stipulated if the clinician and/or investigator feels that a small up-titration is indicated. Up-titrations should not occur during a REASSESS VOLUME STATUS event.

Study drug should be preferentially infused centrally; where no port is available, study drug should **not be** infused into a small peripheral vein or via butterfly catheter.

STOP EVENTS:

1. If HR is ever ≤ 60 bpm, immediately stop infusion for 20 minutes, then restart at half the previous infusion rate, rounded to nearest 10 mcg/kg/min. Do not resume infusion until HR > 70 bpm.
2. If vasopressor dose increases by 0.2 mcg/kg/min norepinephrine (or equivalent) AND doubles within 60 min despite adequate volume expansion, STOP the study drug infusion. Alternatively, if the treating clinician believes that the shock is worsening significantly, STOP the study drug infusion. Do not resume without explicit approval of study physician.
3. If cardiogenic shock develops ($ScvO_2 \leq 60\%$ OR LV Ejection Fraction $\leq 25\%$ OR Cardiac Index ≤ 2.0 L/min/m²), STOP the study drug infusion. Do not resume without explicit approval of study physician.
4. If clinically apparent bronchospasm develops, STOP the study drug infusion. Do not resume.
5. If Grade 2 or Grade 3 heart block develops, immediately STOP the study drug infusion. Do not resume.

REASSESS VOLUME STATUS EVENTS:

When markers of potential preload deficit occur (urine output < 0.5 ml/kg/hr OR vasopressor dosage increase), immediately EVALUATE FOR VOLUME RESPONSIVENESS. A vasopressor dosage increase is defined as at least 0.05 mcg/kg/min absolute AND 20% relative increase in the norepinephrine (or equivalent) infusion.

Titrate vasopressors as per local practice to maintain MAP ≥ 65 mmHg. Norepinephrine is the preferred primary vasopressor.

